Official Title:

Assessment of Inspiratory Effort and Diaphragmatic Function Across Pressure Support Levels in Surgical ICU Patients: A Prospective Physiological Study

ClinicalTrials.gov Identifier (NCT Number):

NCTXXXXXXX

Document Date:

17th September 2025

Title Assessment of Respiratory Drive and Inspiratory Effort Across Pressure Support Levels in Patients After Major Abdominal Surgery: A Physiological Observational Study

Background

Pressure support ventilation (PSV) is one of the most used modes of partial ventilatory assistance in critically ill patients, such as those recovering from acute respiratory failure, major surgery, or during weaning from mechanical ventilation ^(1,2). In PSV, tidal volume (V_t) is the result of a dynamic interaction between patient-generated inspiratory effort and ventilator-delivered pressure. While this mode aims to unload respiratory muscles and preserve spontaneous breathing, inappropriate levels of support—whether too low or too high—may contribute to patient harm⁽³⁾.

Patients undergoing major abdominal surgery⁽⁴⁾ often experience significant physiological changes that impair respiratory function, including reduced diaphragmatic excursion, decreased lung compliance, and impaired cough and secretion clearance due to postoperative pain, abdominal splinting, and the effects of anesthesia. These changes can persist for days, increasing the risk of atelectasis, ventilator-associated complications, and delayed weaning^(5,6). In this context, carefully titrated PSV is essential to provide sufficient support while avoiding over-assistance that may promote diaphragm disuse ^(3,7,8) or under-assistance that may lead to excessive respiratory effort and patient self-inflicted lung injury (P-SILI).^(3,9,10)

Traditional parameters such as V_t and respiratory rate alone are insufficient to evaluate the patient's contribution to breathing effort. The gold standard for measuring inspiratory effort remains esophageal pressure (Pes) monitoring, which allows estimation of the work of breathing and transpulmonary pressure ^(1,11,12). Alternatively, the electrical activity of the crural diaphragm (EAdi) has been proposed as a surrogate for respiratory drive and effort ⁽¹³⁾. However, both methods are limited by their invasiveness, cost, and technical complexity, which limits their feasibility in routine practice.

Given these limitations, several simpler bedside tools have emerged, including occlusion pressure at 0.1 seconds (P0.1), maximum negative occlusion pressure (Pocc), and the pressure muscle index (PMI). P0.1 (airway occlusion pressure measured during the first 100 milliseconds of inspiration) is a useful screening tool for assessing respiratory drive, whereas Pocc (the maximum negative pressure during an inspiratory occlusion) and PMI (a derived measure estimating inspiratory effort) may better reflect inspiratory effort ^(1,3,14,15). Low PMI or a lack of inspiratory pressure plateau may indicate over-assistance, while high Pocc values suggest excessive effort and under-assistance^(1,3,14).

Importantly, no prior studies have specifically investigated how respiratory parameters change in response to pressure support level adjustments in the postoperative setting following major abdominal surgery. To date, only two relevant studies exist: Docci et al. (2023)⁽⁷⁾ conducted a physiological study in patients recovering from acute respiratory failure, examining the impact of PSV level changes on PMI, Vt, and related variables. Another earlier study by Umbrello et al. (2015)⁽¹⁶⁾ included a broader population of post-major elective surgery patients (10 of whom had undergone abdominal surgery), evaluating the correlation between diaphragm ultrasound and traditional effort indices during varying PSV levels. Neither study focused exclusively on the unique postoperative physiology of major abdominal surgery patients requiring prolonged mechanical ventilation, leaving an important knowledge gap.

Despite these developments, no consensus exists on the optimal PSV level that ensures sufficient ventilatory support while preserving respiratory muscle activity. Docci et al. ⁽⁷⁾ introduced a conceptual model suggesting a patient-specific “adequate PSV window,” wherein patients modulate their effort to maintain a target Vt across a range of support levels. However, data supporting precise bedside criteria or cutoff values for over- or under-assistance remain limited

This study has two primary objectives. First, to evaluate changes in respiratory drive and inspiratory effort—measured by Pocc, PMI, and P0.1—and corresponding Vt across varying levels of pressure support in surgical ICU patients after major abdominal surgery who require prolonged mechanical ventilation (>48 hours)⁽¹⁷⁾. Second, we aim to determine the incidence of inadequate assistance (active, quasipassive)⁽⁷⁾ in patients receiving PSV and explore its association with relevant clinical outcomes.

Study Design

This is a prospective, single-center, observational physiological study conducted in the surgical intensive care unit (ICU). A repeated-measures design is employed to systematically evaluate the effects of pressure support (PS) level adjustments on respiratory effort, drive, and diaphragmatic function in mechanically ventilated patients.

Study Population

Inclusion Criteria

- Adult patients (age ≥ 18 years) admitted to the surgical ICU.
- Recent major abdominal surgery requiring postoperative ICU care
- Receiving invasive mechanical ventilation for more than 48 hours
- Clinically stable, with no plan for extubation within 6 hours of study enrollment.

- Able to tolerate short-term adjustments in pressure support (PS) level as per protocol.

Exclusion Criteria

- Known neuromuscular diseases affecting respiratory muscle function.
- Hemodynamic instability requiring escalation of vasopressor support.
- Severe hypoxic respiratory failure requiring PEEP >10 cmH₂O or FiO₂ >60%.
- Deep sedation (Richmond Agitation-Sedation Scale [RASS] score < -3) or ongoing neuromuscular blockade.
- History of chronic obstructive pulmonary disease (COPD) or other obstructive lung diseases.

Intervention / Protocol

After confirming eligibility and obtaining informed consent (from patients or legally authorized representative), enrolled patients will undergo a standardized stepwise adjustment of pressure support (PS) levels while remaining in pressure support ventilation mode. During the protocol, Automatic Tube Compensation (ATC) will be turned off to avoid interference with respiratory measurements. This protocol was adapted from Doccia et al. ⁽⁷⁾. Measurements will be performed once daily for up to three consecutive days or until the patient is extubated—whichever occurs first.

Pressure Support Steps

Patients will be studied at six PS levels in the following sequence:

[figure not shown]
- Baseline PS (clinically set level)
- Baseline -6 cmH₂O
- Baseline -3 cmH₂O
- Return to baseline PS
- Baseline +3 cmH₂O
- Baseline +6 cmH₂O

The order of the four non-baseline steps will be randomized for each patient using sealed envelopes, while the baseline PS step will be performed first and repeated last to assess measurement reproducibility.

At each pressure support (PS) level, a 2-minute stabilization period will be followed by three consecutive measurements of the following parameters: tidal volume (V_t), respiratory rate, P_{0.1}, P_{occ}, pressure muscle index (PMI), static compliance of the

respiratory system (Crs), and peripheral oxygen saturation (SpO_2). Vt , RR , P0.1 , Pocc , PMI , and Crs will be obtained from the ventilator, while SpO_2 will be recorded from the ICU monitor. PMI will be calculated as $\text{PMI} = \text{Pplat} - (\text{PEEP} + \text{PS})$, and Crs as $\text{Crs} = \text{Crs} = \text{Vt} / (\text{Pplat} - \text{PEEP})$. All values will be averaged across the three readings. **Figure 1. Study**

Protocol Flowchart

Measurements and Outcomes

Primary Outcome

- To evaluate changes in respiratory drive and inspiratory effort—quantified using P0.1, maximum negative occlusion pressure (Pocc), and pressure muscle index (PMI)—across varying levels of pressure support in adult surgical ICU patients after major abdominal surgery.

Secondary Outcomes

- To quantify the incidence of quasi-passive and active response patterns during pressure support ventilation, based on physiological criteria derived from patient responses.
- To assess the relationship between these ventilatory response patterns and clinical outcomes, including duration of mechanical ventilation, ICU length of stay, reintubation or non-invasive ventilation use, and ICU/hospital discharge disposition.

Definition of ventilatory response patterns:

- An active pattern is characterized by relatively stable V_t and plateau pressure despite reductions in pressure support, accompanied by a compensatory increase in PMI—indicating greater patient-driven effort. In contrast, a quasi-passive pattern is marked by a progressive decline in V_t and plateau pressure with little or no change in PMI, suggesting limited patient contribution to ventilation. ⁽⁷⁾
- As no standardized thresholds currently exist, these classifications will be determined post hoc based on individual response trends observed in the study dataset.

Data Collection

All data will be prospectively collected during each predefined pressure support (PS) level (baseline, ± 3 cmH₂O, ± 6 cmH₂O), following a 2-minute stabilization period at each step. The following variables will be recorded:

1. Demographics and Baseline Clinical Data

- Age, sex, height, weight, BMI
- Primary diagnosis and operation
- APACHE II or SOFA score at ICU admission
- Time from intubation to enrollment (hours)
- Baseline ventilator settings (PEEP, FiO₂, baseline PS)
- Baseline arterial blood gas (ABG): pH, PaCO₂, PaO₂, HCO₃⁻, SaO₂

2. Ventilatory and Physiological Parameters (at each PS level)

- Tidal volume (Vt) – measured from ventilator display
- Respiratory rate – measured from ventilator
- Minute ventilation (MV) – calculated
- P_{0.1} – occlusion pressure at 0.1 seconds
- P_{occ} – airway pressure drop during inspiratory hold
- PMI – pressure muscle index calculated as P_{plat} – (PEEP + PS)
- P_{plat} – plateau pressure (via inspiratory hold)
- P_{peak} – peak inspiratory pressure
- Crs – static compliance: Vt / (P_{plat} – PEEP)
- SpO₂ – peripheral oxygen saturation (pulse oximetry)
- EtCO₂ – end-tidal CO₂ if available
- HR and MAP – heart rate and mean arterial pressure (non-invasive or arterial line)
- Use of accessory muscles – observational note
- Signs of distress or dyssynchrony – e.g., paradoxical breathing, anxiety, diaphoresis

4. Post-Protocol Clinical Follow-up

- Duration of mechanical ventilation after study (in hours)
- Need for reintubation or non-invasive ventilation within 48 h
- Total ICU length of stay (LOS)
- ICU and hospital discharge status
- Complications: VAP, barotrauma, unexpected weaning failure

Safety and Tolerability

The protocol allows immediate cessation of PS level changes and return to baseline settings if any of the following occur:

- Respiratory rate >35 breaths/min
- SpO₂ < 90%
- HR > 140 bpm or >30% change from baseline
- Signs of distress: diaphoresis, agitation, anxiety
- Hemodynamic instability

Sample Size

This is an exploratory physiological study using a repeated-measures design. Based on prior literature (Docci et al., 2023; Umbrello et al., 2015), a within-subject difference in

the pressure muscle index (PMI) of approximately 2.0 cmH₂O (standard deviation ~2.5) between pressure support (PS) levels is considered clinically meaningful.

Using a two-sided paired t-test with the following assumptions:

- Alpha (α) = 0.05
- Power (1 - β) = 0.90
- Effect size = 0.8

The calculated minimum required sample size is 20 patients. To improve the precision of subgroup analyses, enhance generalizability, and account for possible dropouts or incomplete data, we plan to enroll a total of 40 patients.

Statistical Analysis

Descriptive statistics will be used to summarize baseline characteristics. Continuous variables will be presented as mean \pm standard deviation or median (IQR), depending on distribution. Categorical variables will be summarized as counts and percentages.

Primary analysis:

- Repeated-measures ANOVA or Friedman test (non-parametric) will be used to assess changes in PMI, Pocc, and P0.1 across PS levels.
- Post-hoc pairwise comparisons will be performed with Bonferroni correction.

Secondary analysis:

- Pearson or Spearman correlation will be used to evaluate relationships between effort indices (PMI, Pocc, P0.1).
- Linear mixed models will explore associations between PS levels and effort parameters, accounting for intra-patient variability.
- The incidence of under- and over-assistance will be described, and logistic regression may be used to assess their associations with clinical outcomes (e.g., prolonged ventilation).

A p-value <0.05 will be considered statistically significant. Statistical analyses will be performed using R.

Ethical Considerations

- Study protocol to be approved by institutional ethics board.
- Written informed consent obtained from patient or surrogate.
- Minimal risk as PS level adjustments are brief and within clinically accepted ranges.

References

1. van Oosten JP, Akoumianaki E, Jonkman AH. Monitoring respiratory muscles effort during mechanical ventilation. *Curr Opin Crit Care*. Feb 1 2025;31(1):12-20. doi:10.1097/mcc.0000000000001229

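### The protocol gives two incompatible orders for the pressure-support steps, a listed sequence and a randomised order, and no readable text says which governs

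*Protocol*

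**What the plan says.** In the Protocol, Pressure Support Steps, the list of steps is introduced by "Patients will be studied at six PS levels in the following sequence". Its entries, in order, are baseline, baseline -6, baseline -3, "Return to baseline PS", baseline +3 and baseline +6 cmH2O.

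The paragraph after the list gives a different rule. For the levels other than baseline it states: "The order of the four non-baseline steps will be randomized for each patient using sealed envelopes". For baseline itself the instruction is that "the baseline PS step will be performed first and repeated last to assess measurement reproducibility".

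The Data Collection section names the levels (baseline, ±3, ±6) without an order and allows 2 minutes of stabilisation at each step. Under Statistical Analysis the primary analysis is: "Repeated-measures ANOVA or Friedman test (non-parametric) will be used to assess changes in PMI, Pocc, and P0.1 across PS levels". No term for step position or time is mentioned there.

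**The concern.** The order of the steps is a bedside instruction that protects the primary comparison, and it is stated in two ways that cannot both be followed. The list is called a sequence, and its fourth entry is worded as a return, so it reads as an order and not merely as a set of levels. The next paragraph randomises the four non-baseline levels and moves the repeat baseline to the end.

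The choice matters because effort and drive may change during a session for reasons other than PS: fatigue, arousal, sedation wearing off, or incomplete settling after the previous step. Randomising the order keeps such changes from favouring any one of the four non-baseline levels. Under the listed order, PS rises steadily from step 2 to step 6, so a change over time and a response to PS look the same in PMI, Pocc and P0.1.

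**Working it through.** **1. Can the two rules agree?**

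| Step | Listed order | Randomised rule |
|---|---|---|
| 1 | baseline | baseline |
| 2 | -6 | one of the four levels |
| 3 | -3 | one of the four levels |
| 4 | baseline | one of the four levels |
| 5 | +3 | one of the four levels |
| 6 | +6 | baseline |

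The randomised rule allows 4! = 24 orders. All have a non-baseline level at step 4 and baseline at step 6. The list has baseline at step 4 and +6 at step 6, so it matches 0 of 24. One of the 24 does take the four levels in the order -6, -3, +3, +6, but it still puts the repeat baseline last.

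**2. How closely would the list tie PS to time?**

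Positions are 1 to 6 (mean 3.5) and levels are 0, -6, -3, 0, 3, 6 (mean 0).

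- Sum of products: -12 - 9 + 15 + 36 = 30.
- Sums of squares: 17.5 for position, 36 + 9 + 9 + 36 = 90 for level.
- Correlation over all six steps: 30 / sqrt(17.5 × 90) = 0.76.
- Over steps 2 to 6 the level rises by 3 at each step, so the correlation is exactly 1.00.

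**3. What bias would drift cause under the list?**

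With a linear drift of δ cmH2O per step, the bias is δ times the difference in position: 4δ for +6 (step 6) versus -6 (step 2), and 2δ for +3 (step 5) versus -3 (step 3). The documents give no drift rate. Assuming δ between 0.1 and 0.5, the bias in PMI is 0.4 to 2.0 for +6 versus -6 and 0.2 to 1.0 for +3 versus -3. The upper end is extreme: 0.5 per step is 2.5 cmH2O from first step to last, more than the 2.0 that the Sample Size section calls meaningful.

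**4. Could it be repaired afterwards?**

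Only in part. Under the list, the one level seen at two positions is baseline (steps 1 and 4), so the drift estimate is (second baseline - first baseline)/3. Let s² be the residual variance at one step, equal and independent across steps.

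- Unadjusted variance of a difference between two levels: 2s².
- Adjusted, +6 versus -6: 2s² + 4² × 2s²/9 = 2s²(1 + 16/9), a ratio of 2.78.
- Adjusted, +3 versus -3: 2s²(1 + 4/9), a ratio of 1.44.

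For PMI, the Sample Size section gives a difference of 2.0 with SD about 2.5 for a paired t-test, effect size 0.8. Reading 2.5 as the SD of the paired difference fits the stated minimum of 20: the exact power is 0.909 at 19 patients and 0.924 at 20. With the planned 40 patients, all complete:

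- Unadjusted 95% half-width: 2.023 × 2.5 / sqrt(40) = 0.80 cmH2O.
- Adjusted: 0.80 × sqrt(2.78) = 1.33 cmH2O.

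Five level means and one linear drift term use all six positions, so curved drift could not be separated from PS. Nor could carry-over among the four non-baseline levels, because each would always follow the same step: -6 after baseline, -3 after -6, +3 after baseline, +6 after +3. More patients or further daily sessions in the same order would not help.

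**The case against.** The strongest reply is that the harm arises only on the less likely reading. The randomisation paragraph comes after the list, is explicitly about order, names a mechanism (sealed envelopes) and gives a reason for repeating baseline last. It would have no purpose if the list governed, whereas the list can still serve as an inventory of levels. Staff holding envelopes would probably use them. This stands, and it limits the seriousness of the point. It does not remove the contradiction, because no readable text ranks the two rules.

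A second reply is that a figure is missing from the readable text just after the words that introduce the list, so those words may point to the figure. That is possible, and the flowchart is not faulted here. But the entry for a return to baseline in fourth place still conflicts with a repeat baseline performed last, whatever the figure shows.

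A reader might also infer that the protocol is at fault for not saying which baseline (first, last or mean) enters the analysis. The documents do not support that as a finding: such a choice commonly belongs in the SAP, which is not shown, and the protocol gives the repeat its own purpose, reproducibility. Averaging the two baselines would not be a full safeguard either. Their mean position is (1 + 6)/2 = 3.5, the expected position of the randomised levels, so linear drift cancels from contrasts with baseline. The mean squared position is (1 + 36)/2 = 18.5 for the baselines but (4 + 9 + 16 + 25)/4 = 13.5 for the other four, so quadratic drift does not cancel.

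**Conclusion.** The protocol contradicts itself on the order of the steps, and the wording should be corrected. That conclusion rests on the text alone. The consequences are conditional on the list being followed: correlation of PS with position of 1.00 over steps 2 to 6 and 0.76 over all six, and a variance ratio of 2.78 for +6 versus -6 after adjustment for linear drift. The half-widths of 0.80 and 1.33 cmH2O further assume 40 complete patients and a paired SD of 2.5, which the protocol gives for PMI only.

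A reader might infer that the primary analysis is confounded, or that it will show false PS effects at some known rate. Neither is supported. The randomised order is probably the one intended, and under it drift is balanced in expectation among the four non-baseline levels. The documents give no drift rate, so no error rate can be attached. Nor can one say that every level would have a fixed predecessor under the list: the four non-baseline levels would, but the two baseline steps would not.

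**What to change.** Make the randomised order the only one. Replace the introductory sentence and the ordered list with:

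*Baseline PS is measured first and repeated last; between them, baseline -6, -3, +3 and +6 cmH2O are applied in an order randomised for each patient by sealed envelope.*

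Then check that the flowchart shows the same order. The choice of baseline for the analysis can be left to the SAP, with a note that averaging the two removes only linear drift from contrasts with baseline.

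The cost is a wording change in one section and a check of one figure. It is best made before sessions are run, since data collected in the listed order could be repaired only in part.

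### The primary test needs complete step sequences in a protocol that can leave some incomplete, while the mixed model that could use partial sequences is only secondary

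*Protocol*

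**What the plan says.** Under Pressure Support Steps (Protocol), every step is defined relative to "Baseline PS (clinically set level"). The reduced steps are 3 and 6 cmH2O below it, the latter listed as "Baseline -6 cmH₂O". Baseline comes first and is repeated last, and "The order of the four non-baseline steps will be randomized for each patient using sealed envelopes". Under Data Collection, "All data will be prospectively collected during each predefined pressure support (PS) level".

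Two Inclusion Criteria bear on whether the steps can be delivered: "Clinically stable, with no plan for extubation within 6 hours of study enrollment" and "Able to tolerate short-term adjustments in pressure support (PS) level as per protocol". Neither gives a minimum PS. Under Intervention / Protocol, "Measurements will be performed once daily for up to three consecutive days or until the patient is extubated".

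Safety and Tolerability allows the PS changes to be stopped at once, with a return to baseline, for a respiratory rate above 35, SpO2 below 90%, heart rate limits, distress or haemodynamic instability. Sample Size gives incomplete data as one reason for enrolling 40 patients against a calculated minimum of 20.

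Statistical Analysis names repeated-measures ANOVA or Friedman as the primary analysis of PMI, Pocc and P0.1, with Bonferroni-corrected pairwise comparisons. Linear mixed models of effort on PS level appear under secondary analysis.

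**The concern.** In standard form, both primary tests take a patient or session only if every step is present. One missing step removes the other steps of that sequence from the omnibus test as well.

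The missing steps would not arise at random. A sequence stopped for tachypnoea, desaturation or distress belongs to a patient who tolerated a step poorly. A -6 step that cannot be set belongs to a patient on low support. The study sets out to describe inadequate assistance, and it classifies an active response by stable tidal volume and "plateau pressure despite reductions in pressure support". Dropping these sequences would move the primary result towards patients who tolerate the steps well and have enough support to take away. The protocol already plans a model that can keep partial sequences, but gives it a secondary, exploratory role.

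**Working it through.** **1. The plan's own figure.** Inputs from Sample Size: difference 2.0 cmH2O, SD about 2.5, two-sided alpha 0.05, power 0.90. Effect size = 2.0/2.5 = 0.8. The normal approximation gives ((1.960 + 1.282)/0.8)² = 16.4. The exact paired t-test (noncentral t) needs 19 patients (power 0.909), and 20 patients give 0.924. The stated minimum of 20 is reproduced closely enough.

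**2. Which steps can be set.** Assumption: PS cannot go below 0. The six measurements are baseline, -6, -3, +3, +6 and repeat baseline.

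| Baseline PS (cmH2O) | Steps that cannot be set | Measurements possible | PS span (cmH2O) |
|---|---|---|---|
| 6 or more | none | 6 of 6 | 12 |
| 3 to 5 | -6 (for example 5 - 6 = -1) | 5 of 6 | 9 |
| below 3 | -6 and -3 (for example 2 - 3 = -1) | 4 of 6 | 6 |

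**3. What a safety stop leaves.** Baseline is first and repeat baseline last, so the -6 step falls at position 2 to 5. A sequence stopped there already has 1 to 4 measurements. This route needs no low baseline.

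**4. What a complete-block test would set aside.** Let k of 40 patients have a baseline of 3 to 5, with one session each (k is assumed; the protocol gives no distribution). Deliverable measurements = 240 - k; those leaving the omnibus test = 5k.

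- k = 0: none
- k = 2: 10/238 = 4.2%
- k = 4: 20/236 = 8.5%
- k = 8: 40/232 = 17.2%

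**5. How large a selection effect would have to be.** The mean contrast in the patients kept differs from that in all patients by (share lost) × (difference in contrast between kept and lost). Take a shift of 0.2 cmH2O, which is 10% of the 2.0 called clinically meaningful. The differences in contrast are assumed.

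- Difference of 2 cmH2O: share = 0.2/2 = 10%, or 4 of 40 patients
- Difference of 1 cmH2O: share = 0.2/1 = 20%, or 8 of 40 patients
- 2 patients with a difference of 2: shift = 2/40 × 2 = 0.1

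This applies to contrasts that the lost patients did supply, such as +3 or +6 against baseline.

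**6. Power.** Paired t-test, effect size 0.8. The Bonferroni column uses 10 pairs (five distinct levels), so alpha = 0.005.

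| Complete patients | Alpha 0.05 | Bonferroni, 10 pairs |
|---|---|---|
| 40 | 0.999 | 0.977 |
| 36 | 0.997 | 0.957 |
| 32 | 0.992 | 0.923 |
| 28 | 0.983 | 0.867 |
| 20 | 0.924 | 0.655 |

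With 10 pairs, 90% power needs 31 complete patients, so losing more than 9 of 40 falls below it. If all six steps are compared (15 pairs), the requirement is 33.

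**The case against.** The best case for the plan has four parts.

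- **The flowchart is not shown and may hold a floor.** This stands. A reader might infer that the protocol sets no lowest PS and will enrol patients it cannot study at -6. The documents do not support that: only the visible text lacks a floor, and the tolerance criterion can be read as excluding a patient whose -6 step cannot be delivered. Nor does the text say that support falls from day to day. The low-baseline route may affect nobody.
- **Handling of partial sequences may be in a SAP.** This stands in part. The protocol nowhere prescribes complete-case deletion, and it would be wrong to read it as doing so. But it does fix which analysis is primary. A repeated-measures ANOVA could be fitted as a mixed model, yet the protocol lists mixed models separately as secondary.
- **The data are not lost to the study.** This is correct and limits the harm. Pairwise comparisons can use available pairs, the secondary model can keep every step, and a patient with an incomplete session may have a complete one on another day.
- **The study is exploratory, so the choice of primary method is a preference.** This stands only in part, because the protocol itself foresees stopped sequences and incomplete data.

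A reader might also imagine staff running PS 0 under the -6 label. Nothing in the text suggests it, and calculating PMI already requires the PS at each step, so no bias is estimated for it.

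**Conclusion.** The point holds as a mismatch between design and primary analysis, and is worth considering before data collection. It rests mainly on the safety stops and on the protocol's own expectation of incomplete data, and would remain if every baseline were 6 or more. The unsettable step is a second, conditional route.

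Its size is open. The documents give neither the stopping rate nor the distribution of baseline PS. In the low-baseline illustration, 4.2% to 17.2% of deliverable measurements leave the omnibus test for 2 to 8 affected patients. A shift of 0.2 cmH2O in a PMI contrast would need 4 to 8 of 40 patients with clearly different responses. With two patients and a difference of 2 cmH2O, it is 0.1.

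A reader might infer that the study is underpowered. The figures do not support that at the design alpha: even 20 complete patients give 0.924. Only the Bonferroni pairwise tests are sensitive, and only once more than 9 of 40 patients are incomplete. The concern is who is left out, not how many remain. It assumes the standard complete-block form of both tests.

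**What to change.** Make the planned linear mixed model the primary analysis of PMI, Pocc and P0.1, with a patient random effect, the delivered change in PS, and all available steps, including those from stopped sequences. Keep repeated-measures ANOVA or Friedman on complete sequences as a sensitivity analysis. A baseline-PS interaction and a curved term are optional.

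If the flowchart does not already do so, add one sentence giving a lowest PS for the reduced steps, with the value chosen by the investigators, or a minimum baseline PS. Apply it at every daily session and record the PS actually delivered. A minimum baseline of 6 is transparent but narrows the population.

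The cost is that sentence and an exchange of primary and sensitivity analysis; baseline PS is already collected, and PS at each step is needed for PMI. The downside is reliance on the model's form and on the missing steps being explained by the observed ones. That second assumption is not certain when a step is stopped because of the response to it. The model cannot supply a -6 result that was never delivered.

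### No balancing of the randomised step order is stated and no listed analysis includes step position: a cheap refinement with a small gain, against noise rather than bias

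*Protocol*

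**What the plan says.** The protocol's section Pressure Support Steps describes the order twice. It first says "Patients will be studied at six PS levels in the following sequence" and lists baseline, −6, −3, return to baseline, +3 and +6 cmH₂O. It then says "The order of the four non-baseline steps will be randomized for each patient using sealed envelopes". Baseline is exempt from this: it opens the session and is run again at the end, as a check on reproducibility. How the orders in the envelopes are generated is not stated.

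At each step, "a 2-minute stabilization period will be followed by three consecutive measurements". Under Intervention / Protocol, "Measurements will be performed once daily for up to three consecutive days or until the patient is extubated". Whether a new order is drawn each day is not stated.

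The primary analysis is a repeated-measures ANOVA or Friedman test across support levels, with Bonferroni-corrected pairwise comparisons. In the secondary analysis, "Linear mixed models will explore associations between PS levels and effort parameters, accounting for intra-patient variability". Step position, sequence and carry-over are named in none of these.

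**The concern.** Four steps have 24 possible orders. If 40 patients each receive an independently drawn order, the four levels will not be spread evenly over the positions in the session, or over the levels that precede them. Steps are short and follow one another closely, so effort may drift over the session for reasons unrelated to support level. Uneven positions then pass some of that drift into the estimated differences between levels. With no position term in the model, the drift also stays in the residual. What is at stake is precision in the contrasts that form the primary outcome.

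The timing matters. A position term can be added at any point before analysis, but the orders cannot be rebalanced once they have been used.

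**Working it through.** **Inputs.** From the protocol's Sample Size section: a PMI difference of "approximately 2.0 cmH₂O (standard deviation ~2.5) between pressure support (PS) levels", alpha 0.05, power 0.90, effect size 0.8, minimum 20 patients and 40 planned. From Pressure Support Steps: four randomised steps in positions 2 to 5, with baseline in positions 1 and 6. The size of the drift is not in the documents. It is assumed linear, common to all patients, and 0.5 to 3 cmH₂O in total over the five intervals from step 1 to step 6.

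**The plan's own figure.** 2.0/2.5 = 0.8. The normal approximation gives ((1.960 + 1.282)/0.8)² = 16.4, so 17. Exact paired-t power (noncentral t) gives n = 19 (power 0.909), and n = 20 gives 0.924. The stated 20 is reproduced to within one patient.

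**Imbalance under independent draws.** A given level goes first with probability 1/4, so it does so 10 times in 40 on average; simulation gives a 95% range of 5 to 16. For two levels, the position difference is ±1, ±2 or ±3 in 6, 4 and 2 of the 12 ordered placements. Its mean is 0 and its variance is (6×1 + 4×4 + 2×9)/12 = 40/12 = 10/3. Over 40 patients the mean position difference has SD √((10/3)/40) = 0.289 steps.

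**Effect on a contrast between two randomised levels.** With drift g per step (total/5), the variance of a paired difference is 6.25 + (10/3)g², and SE = √(variance/40). Power is for a difference of 2.0 cmH₂O. Alpha 0.005 is 0.05/10, for the ten pairs among five distinct levels.

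| Total drift (cmH₂O) | g | Added variance | SE | Rise in SE | Power, alpha 0.05 | Power, alpha 0.005 |
|---|---|---|---|---|---|---|
| 0, or drift removed | 0 | 0 | 0.3953 | – | 0.9985 | 0.9768 |
| 0.5 | 0.1 | 0.033 | 0.3963 | 0.3% | 0.9985 | 0.9761 |
| 1 | 0.2 | 0.133 | 0.3995 | 1.1% | 0.9982 | 0.9739 |
| 2 | 0.4 | 0.533 | 0.4118 | 4.2% | 0.9972 | 0.9641 |
| 3 | 0.6 | 1.200 | 0.4316 | 9.2% | 0.9947 | 0.9440 |

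The chance shift in such a contrast has mean zero and SD 0.289g, that is 0.029, 0.058, 0.115 or 0.173 cmH₂O, against the 2.0 target.

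**Check by simulation** (4,000 runs, 40 patients, the four randomised steps only, their four slots as a factor where position is modelled). At total drift 3 the SE was 0.436 with independent orders and no position term, 0.402 with independent orders and a position term, and 0.397 with a Williams square. The mean estimates were 1.997 to 1.999 against a true 2.0. At drift 0 to 1 all options lay between about 0.39 and 0.40.

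**What balance gives.** Four Williams sequences contain 4 × 3 = 12 neighbouring pairs, each ordered pair once. With 40/4 = 10 patients per sequence, every level stands 10 times in each slot and follows each other level 10 times.

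**How position can enter the model.** Baseline occupies only positions 1 and 6, and the other levels only 2 to 5. With position as a six-level factor, the indicators for positions 1 and 6 sum to the baseline indicator. With 40 patients, four level and five position columns, the design has 49 columns and rank 48, so no baseline contrast is estimable. A single linear column gives 40 + 4 + 1 = 45 columns and rank 45. The mean baseline position, (1 + 6)/2 = 3.5, equals the mean of positions 2 to 5, so with both baselines in the model linear drift does not tilt the baseline contrasts either.

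**The case against.** A reader might infer that the protocol prescribes unrestricted draws. It does not. It is silent on how the envelopes are filled, and they could hold a balanced list. The one-sentence description of the mixed model need not list every fixed effect, and a statistical analysis plan that is not shown could add a position term. This stands, and it is why the point is an improvement rather than an error. It does not dispose of the envelope list, which a later analysis plan cannot repair.

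A reader might also infer that the contrasts are biased. Among the four randomised levels they are not: randomisation gives a position difference of mean zero, which is what it is there to do.

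A larger size could be claimed as well. A drift of 1.0 cmH₂O per step would raise the variance by (10/3)/6.25 = 53%. But that is 5 cmH₂O over the session, 2.5 times the difference the protocol calls clinically meaningful, in patients who must be clinically stable to enter. On the SE scale it is √1.533 = 1.24, a rise of 24%. Nothing in the documents supports a drift of that size. The planning SD of 2.5 may also already contain some drift, in which case the table counts it twice.

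Finally, up to three daily sessions would dilute the imbalance if orders are redrawn each day, though not if one order is reused. Sessions stopped under Safety and Tolerability would erode any balance that was set up.

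**Conclusion.** The point holds as a low-cost refinement. No balancing is stated and no listed analysis includes step position. If orders are drawn independently and effort drifts, contrasts among the four randomised levels carry avoidable noise, which raises the SE by 0.3% to 9% for an assumed total drift of 0.5 to 3 cmH₂O. The sample size is not threatened. The result assumes a linear drift common to all patients, one session per patient and an SD of 2.5 free of drift; carry-over was not modelled.

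One contradiction in the same section does not depend on any assumption. The listed sequence, with the return to baseline fourth, does not agree with a randomised order that has baseline first and last. These passages must be reconciled.

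**What to change.** First reconcile the listed sequence with the sentence on randomised order. If the randomised order is what is meant:

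- Fill the sealed envelopes from a four-sequence Williams square for −6, −3, +3 and +6, in blocks of four patients, giving 10 patients per sequence, and say so in the protocol. State whether the order is kept or redrawn on days 2 and 3.
- Add step position (1 to 6) to the linear mixed model as a linear trend, with both baseline steps included. Do not enter it as a six-level factor.

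The two parts do different work. Balance lowers the true variance of the contrasts, but the reported SE falls only when position is also modelled. A position term alone recovers most of the loss.

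The cost is a different list in the envelopes, one degree of freedom, and an assumption that drift is linear. Some balance will be lost when sessions are stopped early. The list must be fixed before enrolment; the model term can follow in the analysis plan.
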